#### **Secondary Analyses:**

Additional analyses will be performed for origin, gender, age, dose level and certain illness characteristics (if there are at least 10 subjects in each treatment group). All subgroup analyses will be considered secondary analyses. Continuous outcomes will be assessed using ANOVA models. The treatment-by-subgroup interaction will be tested to determine whether treatment differences in the continuous outcomes are the same for each subgroup category. The Mantel-Haenszel common odds ratio and the Breslow-Day test for homogeneity of odds ratio will be used to evaluate differences across the subsets for dichotomous categorical outcomes.

**Secondary Outcomes:** *(Hypotheses 2 and 3) PTSD patients randomized to augmentation with riluzole therapy will have significant improvement in depression, anxiety and global functioning compared to those who receive placebo in addition to their pre-study PTSD medication. The NAA/Cr ratio in the hippocampus and anterior cingulate, measured using H MRS, will increase after 8 week treatment with Riluzole.*

The analysis techniques described above will also be employed with the additional secondary outcomes. Further, post-hoc analysis will be performed by the PI in the comparison of outcomes from this research to other PTSD research being conducted by the PI at WRNMMC, including the INTRuST Clinical Consortium. All comparisons will involve de-identified data.

Collaborators from Draper Lab and Brigham and Women Hospital/ Harvard will be responsible for the H MRS data analysis.

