Phase II, indicated as the "Acute Double-Blind Period", in **Figure 1 Riluzole Augmentation for PTSD**, begins after the completion of the stabilization phase, where subjects will be randomized at a ratio of 1:1 to receive an 8-week double-blind treatment of either riluzole or placebo. Riluzole or placebo will be administered in two divided doses (two tablets twice a day). During the clinical trial, all blinded study medication will be manufactured to identical appearance. All members of the research team and treatment staff will be blinded. Subjects will be assessed weekly from Visit 1 through Visit 9 (see Schedule of Events, **Section 5.5.8 Study Time Line**). Riluzole therapy will be initiated at a dose of 50mg twice daily, as will matching placebo for those subjects randomized to placebo. Riluzole may be increased to 200 mg/day thereafter if the subject's weekly case history (subject self-reported symptomatology and CAPS score and/or additional psychological clinical battery diagnostics) indicate that the increased dose may have therapeutic benefit. The maximal allowable dose of riluzole permitted is 200 mg/day. The minimal allowable dose of riluzole permitted is 100 mg/day. Those subjects unable to tolerate the lowest allowable dose will be discontinued from the study. Eligible subjects who consented to participate in the baseline  $^1\text{H}$  MRS portion of the study will undergo a post-treatment scan between visits 8 and 9.

The time commitment for the weekly scheduled visit is estimated to be 2-4 hours. The time commitment for the post-treatment  $^1\text{H}$  MRS scan is estimated to be 60 to 90 minutes.

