### 5.7.1 Data Analysis Table

Independent Variable / Predictor	Dependent Variable/ Outcome	Statistical Test
Riluzole/placebo	PTSD anxiety symptomatology (CAPS total score)	t-test/Mann-Whitney U test
Riluzole/placebo	Clinical Response Rate	Pearson's chi-square test, Fisher's exact test
Riluzole/placebo	Effects of treatment status longitudinally	Regression Analysis
Riluzole/placebo	Origin, gender, age, dose level, illness characteristics	ANOVA, Mantel-Haenszel common odds ratio test, Breslow-Day test
Riluzole/placebo	NAA/Cr ratio	t-test/Mann-Whitney U test
Not Applicable	Not Applicable	Descriptive Statistics

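### Dose level is tested as a subgroup factor alongside gender and age, although it is set after randomisation, so riluzole-placebo contrasts by dose level are not randomised comparisons

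*Combined protocol and SAP*

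**What the plan says.** The Secondary Analyses paragraph of section 11.3 says that "Additional analyses will be performed for origin, gender, age, dose level and certain illness characteristics", subject to the condition "if there are at least 10 subjects in each treatment group". For continuous outcomes, "The treatment-by-subgroup interaction will be tested to determine whether treatment differences in the continuous outcomes are the same for each subgroup category"; for dichotomous outcomes it names the Mantel-Haenszel common odds ratio and the Breslow-Day test. Dose level is not treated differently from the other factors. The Data Analysis Table (5.7.1) groups them in one row, "Origin, gender, age, dose level, illness characteristics", against ANOVA, Mantel-Haenszel and Breslow-Day. Section 11.3 adds that "All subgroup analyses will be considered secondary analyses".

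Dose is described elsewhere:

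- **Start (section 9.5, Phase II):** "Riluzole therapy will be initiated at a dose of 50mg twice daily, as will matching placebo for those subjects randomized to placebo".
- **Increase (same place):** "Riluzole may be increased to 200 mg/day thereafter", depending on the weekly case history, which covers self-reported symptoms, CAPS and/or other scales. The sentence names riluzole only.
- **Decrease (section 14.2):** the higher dose is cut to 100 mg per day if a repeat liver test stays at or above three times the upper limit. Participants already on the low dose are removed. No arm is named.
- **Blinding (section 9.5):** "All members of the research team and treatment staff will be blinded", and the study medication looks identical in both arms.

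Section 10.2 makes change in CAPS the primary efficacy measure. Section 14.1 lists raised liver enzymes among the dose-related adverse events of riluzole.

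**The concern.** Everyone starts at the same level, so dose does not vary at randomisation; all variation in dose level arises afterwards. It comes from early symptom course, which is correlated with the final outcome, and from liver tests, which riluzole itself can raise. Participants at a given dose level in the two arms are therefore not exchangeable, and the 1:1 randomisation does not protect a contrast between them.

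The plan also does not say whether dose level means final, maximum or modal dose, or how a placebo participant's level is recorded. Blinding and identical tablets make a nominal placebo dose likely in practice. If none is recorded, an interaction or stratified odds ratio by dose level cannot be computed. If the 10-participant condition is meant per dose level, the factor would then simply drop out.

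At stake is a reported statement that riluzole works better, or only, at one dose. Readers would take it as a subgroup result of a randomised trial.

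**Working it through.** **The plan's own figure.** Section 11.2 uses a 9-point difference, SD 15, 50 per arm and two-sided α = 0.05. The noncentrality is 9/(15·√(2/50)) = 3.0 with 98 df, and exact power is 0.8439, matching the stated 0.844. This concerns the primary comparison and is unaffected.

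**Anchor for reversed increases.** Section 14.1 describes two open-label riluzole studies. Their sizes follow from the disposition counts: 8 + 3 + 3 = 14, and 13 + 3 + 2 + 1 = 19. Liver tests of about three times the upper limit or more stopped 2 and 1 participants, so 3/33 = 9.1% (exact 95% CI 1.9 to 24.3%).

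**Model (assumed, for illustration).** T = 1 for riluzole and 0 for placebo; d is the true final effect; f is the fraction of it present early.

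- Early improvement = 3 + d·f·T + 12·z₁
- Final improvement = 9 + d·T + 15·z₂, with corr(z₁, z₂) = r between 0.3 and 0.7
- Dose is raised if early improvement is below 9. The rule is the same in both arms, so placebo has a nominal dose.
- A random share q of riluzole increases is later reversed; none on placebo. Removal of low-dose participants is not modelled.

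With c = (6 − d·f·T)/12, p = Φ(c), m_R = −φ(c)/p and m_N = φ(c)/(1−p):

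- mean at final high dose = 9 + d·T + 15r·m_R
- mean at final low dose = 9 + d·T + 15r·[(1−p)m_N + p·q·m_R]/[1 − p(1−q)]

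For placebo, c = 0.5, p = 0.6915, m_R = −0.5092 and m_N = 1.1411. The interaction is the effect at high dose minus the effect at low dose.

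**Case 1: true effect 9 at both doses, q = 0 (or maximum dose used).** For f = 0.5 and r = 0.7, riluzole has c = 0.125, p = 0.5497, m_R = −0.7200 and m_N = 0.8791.

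- High: (18 − 10.5×0.7200) − (9 − 10.5×0.5092) = 10.44 − 3.65 = 6.79
- Low: (18 + 10.5×0.8791) − (9 + 10.5×1.1411) = 27.23 − 20.98 = 6.25

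| f | r | Effect at high | Effect at low | Interaction |
|---|---|---|---|---|
| 0.25 | 0.3 | 8.55 | 8.40 | 0.15 |
| 0.25 | 0.7 | 7.94 | 7.59 | 0.35 |
| 0.5 | 0.3 | 8.05 | 7.82 | 0.23 |
| 0.5 | 0.7 | 6.79 | 6.25 | 0.54 |

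Effects within dose level are diluted, but the interaction is barely disturbed against a standard error of about 5.2 to 6.4 with 50 per arm.

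**Case 2: drug inert (d = 0), final dose used.** For q = 3/33 and r = 0.7, the high-dose means are equal. The riluzole low-dose mean is 9 + 10.5×[0.3085×1.1411 − 0.6915×0.0909×0.5092]/[1 − 0.6915×0.9091] = 18.05, against 20.98 on placebo. The false interaction is 2.93.

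| Share reversed | r = 0.3 | r = 0.5 | r = 0.7 | Rejection at nominal 5% |
|---|---|---|---|---|
| 0 | 0 | 0 | 0 | about 4 to 5% |
| 9% (3/33) | 1.26 | 2.09 | 2.93 | about 5 to 8% |
| 20% | 2.30 | 3.83 | 5.36 | about 6 to 15% |

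Rejection rates come from 20,000 simulated trials of 50 per arm for each setting.

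**Sensitivity, drug inert:**

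- Cut-off of 5 or 15 instead of 9, with 9% reversed: 0.8 to 1.8, or 2.7 to 6.2.
- Placebo increases also reversed at 5%, riluzole at 10%: 0.6 to 1.4. Equal rates: 0.
- Early and final change uncorrelated: 0.
- Improvers escalated instead: −0.3 to −0.7 (9%) and −0.6 to −1.4 (20%), with no excess rejection.
- 30% of dose decisions against the rule: 0.3 to 0.7 (9%) and 0.6 to 1.3 (20%), with rejection about 5 to 6%.

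**The unplanned fallback.** Comparing each riluzole dose group with all placebo, for an inert drug, gives 15r·m_R = −2.3 to −5.3 at the high dose and 15r·m_N = +5.1 to +12.0 at the low dose. That is far worse than the planned test.

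**The case against.** The strongest reply is that little harm follows. Blinded titration probably gives placebo participants a nominal dose, and with maximum dose the interaction test is nearly unbiased. The increase rule is discretionary, so the case with 30% of decisions against a strict cut-off may be closer to practice, and there the excess rejection almost vanishes. Clear inflation needs final dose, a strict rule, many riluzole reversals, few on placebo and a high correlation all together. The 3 of 33 were discontinuations in open-label studies, not dose reductions, and the 20% figure rests only on lying inside a wide interval. The schedule shows CAPS only once between baseline and exit, so most dose decisions would rest on other scales. The analyses are labelled secondary, and no hypothesis in section 9.4 concerns dose. The table in 5.7.1 does not mention an interaction. A definition of dose level might also exist in the legacy protocol, to which several sections refer and which is not among the documents.

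All of this limits the size, and those limits stand. It does not repair the logic. Section 11.3 applies the interaction and stratified tests to dose without exception. Decisions made on other symptom scales still select on a correlate of the outcome. A definition held elsewhere would settle which variable is analysed, but dose would still be set after randomisation. The secondary label says nothing about non-randomised comparison.

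**Conclusion.** The plan is wrong as written on this point: it presents a non-randomised contrast as a subgroup effect, on a variable that the available text does not define. That conclusion follows from sections 9.5, 11.3 and 14.2 and needs no assumption.

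The size does rest on assumptions. In the model above, true effects of 9 are diluted to between 6.2 and 8.6 within dose levels. A spurious interaction ranges from nil to about 3 points at the 9% anchor with the 9-point cut-off (about 6 at a cut-off of 15), and to about 5 points if 20% of riluzole increases are reversed. Whether bias appears turns largely on whether dose level means maximum or final dose, which is the choice left open. The primary CAPS comparison and its power of 0.844 are unaffected. The change should be made, but it does not threaten the trial's main conclusion.

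**What to change.** In 5.7.1 and 11.3, remove dose level from the factors given the treatment-by-subgroup interaction, Mantel-Haenszel and Breslow-Day tests. Before unblinding, define the dose variable (final, maximum or modal) and state how the nominal dose is recorded for placebo participants. Report dose, increases and reductions descriptively by arm. Label any outcome-by-dose result exploratory and non-randomised, not a treatment comparison, and state that riluzole dose groups will not be compared with the whole placebo arm as a substitute.

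The cost is a few lines of analysis-plan wording and the loss of one secondary test that has no causal interpretation. No dosing rule, sample size or primary analysis changes.

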#### 9.5 Study Design:

Describe study design in one to two sentences (e.g., prospective, use of existing records/data /specimens, observational, cross-sectional, interventional, randomized, placebo-controlled, cohort, etc.). Specify the phase – Phase I, II, III, or IV – for FDA-regulated investigational drug research

The study design is a 1:1 randomized, double-blind, placebo-controlled, parallel trial. The ongoing assessment and monitoring of subjects enrolled in the study will be conducted by a Masters-level Clinical Research Psychologist under the supervision of a credentialed provider within the WRNMMV Behavioral

Weight/ Height	X		X								X	Yes
Psychiatric examination	X										X	Yes
Physical examination	X										X	Yes
Chemistry panel and CBC w/dif	X										X	Yes
Thyroid function, HIV, HCG, hepatitis screen and urine drug screen	X										X	Yes
Liver function panel	X		X	X	X	X	X	X	X	X	X	Yes
Menstrual history (women)	X											Yes
Family History Screen	X											Yes
SCID-IV-TR	X											
Placebo lead-in												
Study drug/ Placebo			X	X	X	X	X	X	X	X	X	
Efficacy Measures												
CAPS	X		X					X			X	
CGI,	X		X	X	X	X	X	X	X	X	X	
MADRS	X		X	X	X	X	X	X	X	X	X	
HAM-A			X					X			X	
SDS			X					X			X	
PCL-C			X	X	X	X	X	X	X	X	X	
UKU-SERS-Pat	X		X	X	X	X	X	X	X	X	X	
LSAS			X					X			X	
PSQI, DES			X					X			X	
WHOQOL BREF, CD-RISC			X					X			X	
CTQ			X									
SCL-90			X					X			X	
PDI	X											

Description of Data	Scr	Stabil	V1	V2	V3	V4	V5	V6	V7	V8	V9 a	SOC
Week			0	1	2	3	4	5	6	7	8	
Safety Measures												
Adverse events	X	X	X	X	X	X	X	X	X	X	X	
MRS			X							X		

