## 11.2 Sample Size Estimation:

A power analysis confirms the study will be able to detect a 9 point change in CAPS score in subjects receiving riluzole augmentation versus placebo using a sample size of 50, assuming a two-tailed test, an  $\alpha = 0.05$ , and a standard deviation of 15 (based on the PI's experience in this population seeking treatment at WRNMMC). This yields a power of 0.844. Power increases to 0.909, under the same assumptions, when a single-tailed test is used. The difference value of 9 is considered the minimally clinically significant difference and is supported by recent publications (Krystal et al, 2013; Schnurr et al, 2001; Weathers et al, 2001; Fontana et al, 1997; Norman et al, 2003; Lunney et al, 2007).

The SAS System  
 The POWER Procedure  
 Two-Sample t Test for Mean Difference  
 Fixed Scenario Elements  
 Distribution Normal  
 Method Exact  
 Number of Sides 2  
 Mean Difference 9  
 Standard Deviation 15  
 Group 1 Sample Size 50  
 Group 2 Sample Size 50  
 Null Difference 0  
 Alpha 0.05

Computed Power  
 Power 0.844

The SAS System  
 The POWER Procedure  
 Two-Sample t Test for Mean Difference  
 Fixed Scenario Elements  
 Distribution Normal  
 Method Exact  
 Number of Sides 1  
 Mean Difference 9  
 Standard Deviation 15  
 Group 1 Sample Size 50  
 Group 2 Sample Size 50  
 Null Difference 0  
 Alpha 0.05

Computed Power  
 Power 0.909

To allow for ineligibility (30-40%) and the possibility that more participants will be needed from

WRNMMC (~2:1 ratio), a total of up to 158 participants will be consented study-wide, with up to 104 participants recruited at WRNMMC.

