### 11.3 Data Analysis Plan:

**Primary Analysis:** *(Hypothesis 1) Subjects with PTSD randomized to acute therapy with Riluzole will have a superior response rate acutely compared to subjects randomized to placebo.*

The PI will be primarily responsible for data analysis in this study. He will be assisted by a data analyst or analysts within the Department of Psychiatry at USUHS and this person (or persons) will be added to the protocol as investigators (with IRB approval) prior to any handling of the data. The primary intent of this study is to compare the efficacy of riluzole relative to placebo in the treatment of overall anxiety symptomatology of subjects who have PTSD. This will be analyzed by comparing reductions from baseline scores on the CAPS total score after up to 8-weeks of double-blind therapy to the original score before the start of therapy using t-tests or Mann-Whitney U tests when assumptions for t-tests are not satisfied.

In addition to utilizing the CAPS continuous score, scores will also be dichotomized to examine clinical responders versus non-responders in the treatment and placebo groups. A responder will be defined as any patient who demonstrates a 30% or greater decrease in CAPS total score from baseline (phase I) to the last measured value of Phase II. Response rate analyses will then be performed by comparing the proportion of subjects in each treatment group who met the response criteria. Response rates will be analyzed using Pearson's chi-square test or Fisher's exact test when expected cell sizes are less than 5.

In order to more thoroughly assess the effects of treatment status in a longitudinal setting, random effects regression will also be used to examine the study groups over time in the presence of additional covariates.

In general, variables that are continuous, yet non-normally distributed, will be appropriately transformed or will be analyzed using appropriate non-parametric tests. Variables that are non-continuous (ordinal, nominal) will be analyzed using appropriate non-parametric tests. All tests of hypotheses will be tested at a two-sided a level of 0.05.

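### A non-significant treatment-by-subgroup test cannot determine that effects are the same: with the plan's inputs it misses a 9-point CAPS interaction about 68–78% of the time

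*Combined protocol and SAP*

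**What the plan says.** Section 11.3, under Secondary Analyses, plans analyses by origin, gender, age, dose level and certain illness characteristics, "if there are at least 10 subjects in each treatment group". They are labelled secondary. Continuous outcomes go into ANOVA models, and the purpose of the interaction test is stated directly: "The treatment-by-subgroup interaction will be tested to determine whether treatment differences in the continuous outcomes are the same for each subgroup category". Dichotomous outcomes get a Mantel-Haenszel common odds ratio and a Breslow-Day test. The same techniques carry over to the secondary outcomes.

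The significance level comes from the Primary Analysis part of section 11.3: "All tests of hypotheses will be tested at a two-sided a level of 0.05".

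The only power calculation, in section 11.2, is for the overall treatment comparison: "A power analysis confirms the study will be able to detect a 9 point change in CAPS score in subjects receiving riluzole augmentation versus placebo". It uses "a standard deviation of 15" and 50 subjects in each group. On the size of effect that matters, section 11.2 says: "The difference value of 9 is considered the minimally clinically significant difference".

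The available text gives no power for the interaction test, no interval for the interaction, no equivalence margin, and no statement on what a non-significant interaction may be taken to show.

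**The concern.** A significance test of interaction can give evidence that effects differ. It cannot give evidence that they are the same unless the estimate is precise enough to rule out differences that matter. The plan assigns the test the job of settling whether effects are the same and offers only a p-value to settle it with. In a trial sized for the main effect, the usual outcome is p > 0.05 whether or not the subgroups differ materially.

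At stake is what the report may say about who benefits. If riluzole helped only one category of a subgroup factor, the interaction test would more often than not be non-significant, and nothing in the plan would stop that result being presented as a uniform effect. The exposure is greatest in the smallest subgroups that the 10-subject rule admits, where the test is weakest.

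**Working it through.** **Inputs.** Two-sided alpha 0.05 (section 11.3). Target difference 9 CAPS points, SD 15, 50 per arm (section 11.2). Allocation 1:1 (section 9.5).

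**Assumptions added here.** Two categories per factor; SD 15 in every cell; each category split equally between arms; the 10-subject rule read as 10 per arm in the smaller category, so that 40/10 per arm is the most unequal split allowed.

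**Step 1: reproduce the plan's figure.** SE = 15 × √(1/50 + 1/50) = 3.0. Noncentrality = 9/3.0 = 3.0 on 98 df. The exact noncentral t gives power 0.844, which matches section 11.2. The one-sided variant, 0.909, also reproduces.

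**Step 2: power for the interaction.** The interaction is the treatment difference in category 1 minus that in category 2. With n1 and n2 subjects per arm in the two categories:

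SE = 15 × √(2/n1 + 2/n2), on 2(n1 + n2) − 4 = 96 df.

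The true interaction is set at 9 points: the full target effect in one category and none in the other. The 95% half-width is 1.985 × SE.

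| Split per arm | SE | Noncentrality | Power | Missed | 95% half-width | Interaction with 80% power |
|---|---|---|---|---|---|---|
| 25/25 | 6.00 | 1.50 | 0.318 | 68% | 11.9 | 17.0 |
| 33/17 | 6.33 | 1.42 | 0.290 | 71% | 12.6 | 17.9 |
| 40/10 | 7.50 | 1.20 | 0.221 | 78% | 14.9 | 21.2 |

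Every half-width exceeds 9. Even an estimated interaction of exactly zero would leave a 9-point difference in either direction inside the interval.

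**Step 3: sensitivity to numbers randomised.** Section 11.2 allows for 30–40% ineligibility among up to 158 consented, and section 13.5 says the 158 includes screen failures. That gives 158 × 0.60 = 94.8 to 158 × 0.70 = 110.6 randomised, or about 47 to 55 per arm. The miss rate is then 70% to 65% for equal categories, and about 78% when the smaller category has 10 per arm. With three equal categories and true effects of 0/4.5/9 or 0/0/9, the 2-df F test has power of only about 0.17 to 0.22, so the two-category figures do not overstate the problem.

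**Step 4: chance that the overall test succeeds and the interaction is missed.** If 9 points lie in one category only, the overall effect is 9 × (share of subjects in that category), with SE 3.0. With the same split in both arms, the overall and interaction estimates are independent, so the two probabilities multiply.

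- 25/25: overall effect 4.5, power 0.318; joint 0.318 × 0.682 = 22%.
- 33/17: benefit in the larger category, overall 5.94, power 0.500, joint 35%; in the smaller, overall 3.06, power 0.173, joint 12%.
- 40/10: benefit in the larger category, overall 7.2, power 0.661, joint 52%; in the smaller, overall 1.8, power 0.091, joint 7%.

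Because of the independence, the miss rate remains 68–78% among trials whose overall result is significant.

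**The case against.** The strongest reply is that the plan's sentence is ordinary wording for an interaction test, and that no sentence says p > 0.05 will be reported as sameness. That is correct. A reader might infer that the plan prescribes such a report, or that the trial would go on to state that riluzole works equally in all groups; the documents support neither. They assign the test a purpose it cannot serve and leave the reading of a non-significant result open.

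A reader might also take 68–78% as the chance of a false claim of uniform benefit. It is not. Such a claim would also need a significant overall effect, and the joint probability is about 7–52%, depending on the split and on which category holds the benefit.

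It is also fair to say that the analyses are labelled secondary, that a minimum size is set, that an interaction test is better practice than separate p-values within subgroups, and that low interaction power is normal in a trial of this size. These points limit the consequence. They do not turn a non-significant test into evidence of equality, and low power is the reason to fix the interpretation in advance.

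Two further limits stand. The 78% figure depends on how the 10-subject rule is read. The figures here are for CAPS only: nothing has been calculated for Breslow-Day, where the point rests on the general principle that a non-significant homogeneity test does not establish homogeneity.

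**Conclusion.** The point holds as one about interpretation. At two-sided 0.05, with SD 15, 50 per arm and two categories, the interaction test has power of about 32% (equal categories) down to 22% (10 per arm in the smaller category) for an interaction as large as the trial's whole target effect. The 95% interval extends 12 to 15 CAPS points either side of the estimate. A non-significant result is therefore compatible with a full 9-point effect in one category and none in the other, and cannot determine that effects are the same. An interaction would have to reach about 17 to 21 points, roughly twice the target effect, for 80% power.

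The primary CAPS comparison and its stated power are unaffected, and a larger trial is not called for.

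**What to change.** In section 11.3, Secondary Analyses, replace the interaction sentence with:

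> For each subgroup factor, the treatment effect in each category and the treatment-by-subgroup difference (ratio of odds ratios for dichotomous outcomes) will be estimated with 95% confidence intervals. A non-significant interaction or Breslow-Day test will not be taken as evidence that effects are the same.

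A rule that calls effects consistent only when the interval lies within ±9 CAPS points should not be added. At SD 15 and 50 per arm it could not be met even by an estimate of zero: the observed SD would have to fall below about 11.3 (9 / (1.985 × √(4/25))) at 25/25, or about 9.1 (9 / (1.985 × √(2/40 + 2/10))) at 40/10. A CAPS margin also has no meaning for the other outcomes.

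Stating in section 11.2 that power for a 9-point interaction is about 22–32% would be useful but is optional.

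The cost is a change of wording and a few additional intervals, with no new patients or data. The downside is that most subgroup results will be reported as inconclusive.
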